1. PURPOSE, BACKGROUND, AND OBJECTIVES

1.1. PURPOSE

This is a safety study of a commercially available silver-nylon burn dressing (Silverlon® Dressing, Argentum Medical, Geneva, IL) in a cohort of patients likely to develop radiation dermatitis from undergoing radiation therapy as a treatment for breast cancer. The goal is to establish the safety of the use of Silverlon® as a topical dressing to manage radiation dermatitis. While the results are expected to be applicable to any cancer site requiring radiation therapy, we will select patients with breast cancer as a group most easily studied for radiation dermatitis.

1.2 BACKGROUND AND RATIONALE

Of the 1.6 million patients newly diagnosed with cancer annually in the United States, approximately 50% will receive radiation therapy at some point in their treatment. Up to 95% of these patients will experience adverse skin reactions, collectively termed radiation dermatitis. (1, 2, 3, 4, 5, 6, 7). Up to 60% of patients with breast radiation will develop Radiation Therapy Oncology Group (RTOG) Late Radiation Morbidity Scoring grade 2 or 3 toxicity and 30-40% of unselected patients will develop moist desquamation (8). Because of the almost universal occurrence of radiation dermatitis in patients undergoing radiation therapy, there is great interest in finding skin care products that can prevent or ameliorate this injury while providing an optimal environment to assure safe and effective tissue repair.

Currently, there are no effective products that prevent radiation dermatitis; therefore, emphasis has shifted to treatment of visible signs of sustained radiation-induced skin reaction. Unfortunately, no standard treatment recommendations exist for the prevention of radiation skin toxicity (9). There is 'significant heterogeneity in clinical practice' (10), a 'relative lack of high-quality evidence to support specific management strategies' (10), and no product is universally successful or recognized as best. There are hundreds of products used to treat radiation dermatitis, nearly all being employed 'off-label'. There are approximately 20 products with US Food and Drug Administration (FDA) pre-marketing clearance for the indication of radiation dermatitis. Most are passive protective hydrogel emulsions or dressings. All have been approved through the 'substantial equivalence' 510(k) pathway, without clinical trials in radiation dermatitis prior to approval.

Silver-nylon dressings (Silverlon® Wound/Burn Contact Dressings, Argentum Medical, Geneva IL) are comprised of a single layer of knitted nylon fiber substrate coated with metallic silver. Commercially marketed since 2003, Silverlon® dressings have 16 FDA 510(k) premarketing clearances, with both over-the-counter and prescription indications. Silverlon® dressings have also been the standard US military dressings for burns and traumatic injuries for over 15 years (11) and are the standard of care for transatlantic aeromedical evacuation of burn patients (12,13). Silverlon® Dressings are indicated for use up to 7 days for partial and full thickness wounds including traumatic wounds, surgical wounds (donor and graft sites, incisions), first and second degree thermal burns, as well as dermal ulcers (stage I-IV pressure sores, venous stasis ulcers, arterial ulcers, diabetic ulcers), vascular access or peripheral IV sites, orthopedic external pin sites and wound drain sites. Additionally, Silverlon® Dressings are indicated for the management of infected wounds, as the silver in the dressing provides an antimicrobial barrier that may be helpful in managing these wounds. Silverlon® Dressings are a non-adherent wound contact layer that reduces pain during dressing changes and evaporation of moisture in the dressing may soothe the wound. (14)

Page 5 of 41 RSRB STUDY00004587 Version Date: 09/14/2021 NCT04238728 Several clinical studies performed in Canada have demonstrated the utility of silver-nylon dressings in the management of radiation dermatitis. Vuong et al (15) performed a Phase II study of 15 patients with anal or gynecologic cancers who received radiation therapy of 45-54 Gy in 25-30 fractions with concurrent chemotherapy. In this population, the expected incidence of radiation dermatitis is 100% with 43-78% of patients progressing to severe (RTOG grade 3-4) radiation dermatitis (15). Silver-nylon dressings were placed starting on day 1 of radiation therapy and maintained continuously until 2 weeks after conclusion of the radiation therapy. Dressings were removed during radiation application and for bathing. A control group received silver sulfadiazine starting at the occurrence of symptomatic dermatitis. The mean RTOG radiation dermatitis severity score was 1.15 (SD= 0.4) for silver nylon group compared to 2.62 (SD 0.48) in the control group (p < 0.0001).

A follow-up Phase III study by Niazi et al (16) had similar results. Forty-two anal or rectal cancer patients undergoing high-dose radiation therapy of 50 to 60 Gy in 28-33 fractions with concurrent chemotherapy were randomized to silver-nylon or silver sulfadiazine treatment. Silver-nylon dressings were placed on day 1 of therapy and continued until 2 weeks post-therapy. Silver sulfadiazine was started at the occurrence of grade 1 radiation dermatitis. The Silver-nylon group RTOG scores at the end of radiation treatment were significantly lower than the silver sulfadiazine group (1.67 vs. 2.53, p= 0.01). The silver-nylon group also had fewer and shorter breaks in treatment than the control group (16).

Studies in head/neck cancer and breast cancer have yielded less clear results because of methodologic flaws. Vavassis et al (17) evaluated silver-nylon dressings in 12 patients with squamous carcinoma of the head and neck undergoing radiation therapy. Silver-nylon dressings were placed on one side of the neck and silver sulfadiazine on the contralateral side of the neck. Silver-nylon dressings and silver sulfadiazine were initiated at the point where radiation dermatitis was assessed as RTOG grade 2 or greater. Nine of the 12 patients developed radiation dermatitis of RTOG grades 3 or 4. There was no difference in improvement in RTOG grade between control (silver sulfadiazine) and silver-nylon sides. Pain control was subjectively better in the silver-nylon side for 8 of 12 patients. Furthermore, half (6/12) of the patients stopped using silver sulfadiazine and applied silver-nylon to both sides of the neck because of better pain control.

Aquino-Parsons et al (8) studied silver-nylon dressings in 196 breast cancer patients undergoing radiation therapy of either 42.5 Gy in 16 fractions over 22 days or 45 Gy in 25 fractions over 33 days with a boost dose to the tumor bed. The experimental arm used silver-nylon dressings on the inframammary fold continuously placed except during radiation therapy and bathing, starting at day 6 of radiation therapy and continuing until 14 days after completion of therapy. The control group used twice-daily application of moisturizing cream (with brand chosen by the patient), along with topical steroids for pruritis or brisk erythema, and saline compresses, hydrogel or silver sulfadiazine for moist desquamation. Moist desquamation occurred in 38% of patients with no difference in incidence, size or RTOG score of moist desquamation between treatment and control arms. Patients reported less itching in the silver-nylon arm at completion of the course of radiation therapy and at one week afterwards. The methodologic flaws of this study included withholding treatment until day 6 of radiation therapy and using the silver-nylon dressing only on the inframammary fold rather than on the entire radiated field.

Page 6 of 41 RSRB STUDY00004587 Version Date: 09/14/2021 NCT04238728

Based on US Military experience and utility for multiple injury conditions, the Department of Health and Human Services / Biomedical Advanced Research and Development Authority (BARDA) has placed Silverlon® in the National Stockpile, and, since 2013, has funded multiple preclinical studies to broaden FDA-cleared indications for mass-casualty use. In July, 2019, Silverlon® obtained the first-ever FDA clearance for the treatment of sulfur-mustard chemical weapons burns. BARDA and Argentum maintain an active research program seeking FDA clearance for radiation injuries including porcine preclinical studies of cutaneous radiation syndrome. The present study, part of the BARDA radiation effort, seeks to perform clinical studies leading to FDA clearance for the indication of radiation dermatitis. Our previous research in multiple animal models (rat, hairless guinea pig, Gottingen minipig), multiple wound types (thermal burns, chemical burns and open wounds), and several different wound depths (superficial partial thickness, deep partial thickness and full thickness) demonstrate that there is no adverse or systemic effect of topical silver nylon therapy. In all animal studies, following extended application of Silverlon® dressings, silver ion was not detectable in blood, spleen, liver or kidney samples obtained at autopsy. (18,19) The present study, a small human safety study of topical application of silver-nylon dressings to patients undergoing radiation therapy, is intended to complete our extensive safety experience with silver nylon dressings in support of an FDA 510(k) application for the additional indication for human radiation dermatitis.

1.3. OBJECTIVES

Primary Objective: To investigate the safety of Silverlon® dressing in patients throughout their prescribed course of radiation therapy and after radiation therapy.

- Hypothesis: We do not expect any adverse effects from extended use of Silverlon® dressing during and after radiation therapy.
- Primary Outcome Measures: Adverse reactions/events documented by the radiation oncologist as "probable" or "definite" related to Silverlon® Dressing (Weekly AE/Chart Review Source Doc).

Secondary Objective: To evaluate the feasibility of managing radiation dermatitis with Silverlon® dressing.

- Hypothesis: We expect that Silverlon® will be a feasible therapeutic modality for managing radiation dermatitis. We expect high compliance rate during RT and slightly lower when skin symptoms are not presented (i.e., before RT and post-RT). We do not expect any withdrawals due to adverse reactions to the dressing.
- Secondary Outcome Measures: Compliance; Withdrawal rate due to dressing.

Exploratory Objective: To monitor the severity of radiation dermatitis and patient quality of life during use of Silverlon® dressing throughout radiation therapy and after radiation therapy.

• Exploratory Outcome Measures: radiation dermatitis severity (RTOG Score & Radiation Induced Skin Reaction Assessment Scale (RISRAS)); DLQI

Page 7 of 41 RSRB STUDY00004587 Version Date: 09/14/2021 NCT04238728

[figure not shown]

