7. SUBJECT WITHDRAWALS

Subjects will be advised during the consent process that they have the right to withdraw from the study at any time without prejudice or reason. Subjects that withdraw from the study will be replaced with another subject. Subjects will continue to receive radiation therapy as prescribed with standard of care with their treating radiation oncologist. The reason for discontinuation will be recorded in the subject's medical records. The date of occurrence and reasons for any subject withdrawal will be recorded and documented on the **Withdrawal Form**.

Subjects can be withdrawn from the study by the investigator or radiation oncologist for: non-compliance to study procedures; termination of funding; allergic reaction to Silverlon® dressing; worsening of the disease under study; intercurrent illness; pregnancy; or progression of skin reaction to RTOG score ≥3 in the radiation area where the Silverlon® dressing has been applied (i.e., whole breast). RTOG score ≥3 requires patients to have areas moist desquamation outside of skin fold regions (i.e., which would exclude inframammary fold and axillas because these are skin fold regions). Additionally, an area of moist desquamation that is >50% of the radiation treatment area (i.e., RISRAS-HPA score ≥3). Therefore, a large area of moist desquamation outside of skin folds would suggest withdrawal. Pinpoint areas and fold areas of moist desquamation could not require withdrawal. Patients withdrawn from the study will stop using Silverlon® dressing, but continue to receive radiation therapy on their normal schedule as prescribed by the treating radiation oncologist. For patients withdrawn from the study, standard of care for radiation dermatitis will be provided by the treating radiation oncologist, who will continue to follow the patient as per their normal clinical routine. The date of occurrence and reasons for any subject withdrawal will be recorded and documented on the Withdrawal Form. An adverse event will be reported if the skin reaction is RTOG ≥4. This grade of radiation dermatitis is severe and should be reported on the AE Source Doc and following reporting procedures stated in §10. Allergic reaction to Silverlon® dressing will be reported as an unexpected side effect on the AE Source Doc.

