10.2. RECORDING ADVERSE EVENTS

Study personnel will assess adverse events by recording all voluntary complaints of the subject. Any side effects and adverse reactions will be noted on the AE Source Doc. Study personnel will check with the nurse and/or treating radiation oncologist regarding any reported adverse reactions. All adverse events, whether observed by the Investigator, the treating radiation oncologist, or volunteered by the subject, will be documented. Adverse events will be reported per the University of Rochester Research Subjects Review Board (RSRB) reporting requirements. Each adverse event will include a brief description of the experience, the date of onset, the severity of the event, the relationship to investigational intervention, and any action taken with respect to the study and intervention. Adverse event monitoring will occur at the start of informed consent until completion of the study.

The relationship to the study device and the severity of each adverse event (i.e., attribution) as judged by the investigator or radiation oncologist must also be recorded. An adverse event is any untoward medical occurrence in a subject administered study device, and which does not necessarily have a causal relationship with this treatment. The relationship of each adverse event to the study device must be recorded as one of the choices on the scale below:

DEFINITE: Causal relationship is certain (e.g., the temporal relationship between device use and the adverse event onset/course is reasonable; there is a clinically compatible response to dechallenge; other causes have been eliminated; and the event must be definitive pharmacologically or phenomenologically using a satisfactory re-challenge procedure, if necessary).

PROBABLE: High degree of certainty for causal relationship (e.g., the temporal relationship between device use and the adverse event onset/course is reasonable; there is a clinically compatible response to de-challenge [re-challenge is not required]; and other causes have been eliminated or are unlikely).

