Page 31 of 41 RSRB STUDY00004587 Version Date: 09/14/2021 NCT04238728 POSSIBLE: Causal relationship is uncertain (e.g., the temporal relationship between device use and the adverse event onset/course is reasonable or unknown; de-challenge/re-challenge information is either unknown or equivocal; and while other potential causes may or may not exist, a causal relationship to study device does not appear probable).

UNLIKELY: Not reasonably related, although a causal relationship cannot be ruled out (e.g., while the temporal relationship between device use and the adverse event onset/course does not preclude causality, there is a clear alternate cause that is more likely to have caused the adverse event than the study device).

UNRELATED: No possible relationship (e.g., the temporal relationship between device use and the adverse event onset/course is unreasonable or incompatible, or a causal relationship to the device is not plausible).

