13.2. Statistical Analyses

This is a safety study to determine Silverlon® dressing indication for radiation dermatitis. Descriptive statistics will be used to describe the study subject population. The primary analyses will evaluate the number of adverse events or reactions reported (if any) at the breast irradiation site where the Silverlon® dressing was applied. The primary analyses will be conducted on 30 fully evaluable subjects (i.e., 30 subjects that fully complete the study) and on all subjects that initiated treatment with Silverlon® dressing in an intent to treat analysis (see section 13.1). For a safety study, it is important to obtain the overall adverse event rate for all subjects that initiated treatment and all subjects who fully completed the study.

The secondary analyses will evaluate the compliance rates for the Silverlon® Dressing during RT and post RT. Compliance will be on the number of days during RT and post-RT that the dressing was worn. We expect compliance rate to be 97% (8). Additionally, we will evaluate the percentage of subjects that removed the dressing for sleeping. Subjects are asked to wear the dressing during sleep and only remove the dressing for RT sessions, showering/bathing, or swimming. Furthermore, we will calculate the number of hours during a day that the dressing was not worn summing the time between removal and application of the dressing each day.

Page 34 of 41 Version Date: 09/14/2021 Compliance will be evaluated in the 30 fully evaluable subjects. Although we can and will evaluate compliance in all subjects that initiated treatment, these analyses will not provide a complete picture of compliance due to early termination of study procedures. Furthermore, the secondary analyses will also evaluate withdrawal rates due to the Silverlon® dressing in all subjects who initiated treatment. We expect less than 6 subjects to withdraw due to the Silverlon® dressing. The exploratory analyses will assess trends in radiation dermatitis severity (i.e., RTOG and RISRAS) and quality of life (DLQI) during the course of the study. These analyses will also be able to evaluate changes in skin symptoms experience by the patient based on the RISRAS-Patient Symptom Scale during RT.

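### Sections 1.3, 11 and 13.2 define the primary safety event in three ways, and under the 1.3 attribution filter a zero is only weakly informative about dressing reactions that resemble radiation dermatitis

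*Combined protocol and SAP*

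**What the plan says.** The protocol defines the event behind the primary safety result in three places.

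- **Section 1.3 (Primary Outcome Measures):** "Adverse reactions/events documented by the radiation oncologist as 'probable' or 'definite' related to Silverlon® Dressing". Events rated possible do not count.
- **Section 13.2:** the stated task of the main analysis is to "evaluate the number of adverse events or reactions reported (if any) at the breast irradiation site where the Silverlon® dressing was applied". No attribution level is named.
- **Section 11:** for the purpose of this study, an adverse event is radiation dermatitis of RTOG grade 4 or above, or another reaction of Grade 3 or higher in the dressing area.

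Section 10.1 also gives the usual broad definition of an adverse event, irrespective of cause.

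Section 10.2 illustrates a probable rating by reasonable timing, and adds that "there is a clinically compatible response to de-challenge [re-challenge is not required]; and other causes have been eliminated or are unlikely". Definite is stricter. An event is unlikely where "there is a clear alternate cause that is more likely to have caused the adverse event than the study device".

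On background, section 1.2 says of irradiated patients generally: "Up to 95% of these patients will experience adverse skin reactions, collectively termed radiation dermatitis". Section 2.1 has the dressing cover the whole irradiated breast from the first day of radiation and states that there is no control group. Section 13.1 plans on zero events, with 95% upper limits of 0.116 (n = 30) and 0.097 (n = 36).

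**The concern.** There are two linked problems.

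First, three definitions of the event give three possible primary results, and nothing says which one governs. The planned count of zero in section 13.1 makes sense only for events attributed to the dressing, yet the analysis section does not say so.

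Second, the 1.3 filter is weakest for local reactions that look like radiation dermatitis: erythema, itch, burning, desquamation. Radiation is a ready alternative explanation at the same site. An assessor who follows the section 10.2 criteria will tend to rate such an event possible or unlikely, and it then leaves the primary outcome. De-challenge often gives little help while treatment is under way: "Patients withdrawn from the study will stop using Silverlon® dressing, but continue to receive radiation therapy on their normal schedule". Section 6 also permits standard-of-care topical treatment for subjects withdrawn for skin progression, so the course after stopping is confounded.

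The results are meant to support a 510(k) application for this indication (sections 1.2 and 14). A zero with an upper limit of 0.116 or 0.097 could be read as bounding all skin harm from the dressing. It bounds something narrower.

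**Working it through.** **1. The plan's own figures.** Inputs from section 13.1: 0 events, n = 30 and n = 36, two-sided 95% Clopper-Pearson. With zero events the upper limit is 1 − 0.025^(1/n).

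- n = 30: 1 − 0.025^(1/30) = 0.1157, stated as 0.116.
- n = 36: 1 − 0.025^(1/36) = 0.0974, stated as 0.097.

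Both reproduce.

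**2. What the limits bound.** Let p be the true proportion of subjects with a dressing-caused local reaction, and s the share of those reactions rated probable or definite. The documents give neither, so both are assumptions here. The 1.3 outcome observes events at rate p × s, so the limit applies to p × s. The limit on p is the Clopper-Pearson limit divided by s.

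| Assumed s | Limit on p after 0/30 | Limit on p after 0/36 |
|---|---|---|
| 1 | 0.116 | 0.097 |
| 0.5 | 0.1157/0.5 = 0.231 | 0.0974/0.5 = 0.195 |
| 0.25 | 0.1157/0.25 = 0.463 | 0.0974/0.25 = 0.390 |

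The stated limits bound p only if every true reaction is rated probable or definite.

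**3. How easily a zero arises.** P(0 of 30) = (1 − p × s)^30.

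| Assumed p | s = 1 | s = 0.5 | s = 0.25 |
|---|---|---|---|
| 0.10 | 0.042 | 0.215 | 0.468 |
| 0.20 | 0.001 | 0.042 | 0.215 |

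A zero is more likely than not only when p × s is below 1 − 0.5^(1/30) = 0.023.

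**4. How far the definitions can diverge.** Section 1.2 gives 30–40% moist desquamation in unselected breast patients. In 36 subjects that is 0.30 × 36 = 10.8 to 0.40 × 36 = 14.4, or about 11 to 14. As an illustration, suppose 14 subjects have moist desquamation recorded as an event at the site, none reaches RTOG 4, no other reaction reaches Grade 3, and none is attributed to the dressing:

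- section 13.2 wording: 14/36 = 0.39 (exact 95% CI 0.23 to 0.57);
- section 1.3 wording: 0/36 (0 to 0.097);
- section 11 wording: 0/36 (0 to 0.097).

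The 1.3 and 11 results agree here only by construction. A Grade 2 reaction rated probable counts under 1.3 and not under 11. An RTOG 4 reaction rated unlikely does the reverse.

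**5. Unit of counting.** The section 13.1 table describes the measure as adverse events per number of patients. A Clopper-Pearson interval needs a yes/no result per subject, so the count should be subjects with at least one event.

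**The case against.** The strongest reply is that section 10.2 does not prescribe what it seems to. Its de-challenge and other-cause conditions are introduced as examples, and the section 10.1 table describes probable simply as likely related. Reactions distinguishable from dermatitis, such as an allergic rash, can still be rated probable. De-challenge is not always confounded by radiation either: the adverse event form allows the dressing to be interrupted as well as stopped, and the dressing is worn for two weeks after radiation ends. All of this stands, and it limits the point to reactions that resemble dermatitis.

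A reader might infer more: that local reactions can rarely qualify, so that a zero is largely built in. The documents do not support that, because they give no value for s. At an assumed true rate of 20% with half of reactions attributed, 0/30 has only a 4% chance. Nor should 0.95 × 36 = 34.2 be read as an expected 34 subjects carrying the competing cause. The 95% is a ceiling for irradiated patients of any cancer type.

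It can also be said that worsening skin is captured without attribution through RTOG and RISRAS scores, dressing-related withdrawals, the stopping rule, the weekly questions and the 90-day contact. That is true, and section 14 lets the FDA request individual data. But RTOG and RISRAS are exploratory, withdrawal is secondary, and none of these measures has a comparator. They supplement the primary outcome without repairing its definition.

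Finally, making possible-or-higher the primary threshold has its own cost, since ordinary dermatitis could then count. If 34 of 36 subjects qualified, the result would be 0.94 (0.81 to 0.99), which cannot be interpreted without controls. This is why the fix reports that rate alongside and does not substitute it.

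**Conclusion.** The point holds in two parts. The inconsistency between sections 1.3, 11 and 13.2 is plain on the text and needs no assumption: identical data can produce different primary results. The second part is a limit on interpretation. Under the 1.3 filter, a zero is weakly informative about dermatitis-like dressing reactions, and 0.116 and 0.097 are limits for events rated probable or definite, not for all dressing-caused reactions.

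How weak depends on the unknown attribution share. Under assumed shares of one half and one quarter, 0/30 leaves room for true rates up to about 23% and 46%. These are illustrations, not estimates. The documents do not show that a zero is predetermined.

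**What to change.** - Reconcile sections 1.3, 11 and 13.2 to one primary event definition, and count subjects with at least one event.
- Beside the probable-or-definite result, report with exact 95% intervals (a) the proportion of subjects with an event rated possible, probable or definite, and (b) the proportion with any dressing-site event regardless of attribution.
- State in section 13.1 and in the report that 0.116 and 0.097 apply only to events attributed as probable or definite.
- Do not add a rule that concurrent dermatitis alone can never place an event below possible. It would conflict with the section 10.2 definition of unlikely and would draw ordinary dermatitis into the count.

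The cost is protocol and analysis wording. The adverse event form already records all five attribution levels, so no new visits, forms or subjects are needed. The downside is real: the reported set of rates will no longer be only a zero, and the broader rates will include ordinary radiation dermatitis that cannot be separated from dressing effects without a control group.
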